- Serum creatinine and creatinine clearance exclusion criteria were revised to align with current medical practice and provide consistency across BGJ398 protocols. BGJ398 has not been demonstrated to be nephrotoxic.
- The criteria for drug discontinuation due to asymptomatic increase in lipase have been relaxed. Asymptomatic mild to moderate increases in lipase have been seen with BGJ398 dosing, particularly in patients with cholangiocarcinoma, but there have been no cases of pancreatitis.
- The frequency of ophthalmological assessments was reduced to align with other BGJ398 protocols.
- The statistical methods and data analysis section was revised based on the changes to the inclusion criteria.
- The list of concomitant medications was revised based on the Oncology Clinical Pharmacology Drug-Drug Interaction Database (release date: 29 Oct 2012)

Changes to the protocol

Changes to specific sections of the protocol are shown in the track changes version of the protocol using strike through red font for deletions and red underlined for insertions.

The following changes to the protocol have been made:

- Updated Protocol Summary with the revisions to inclusion criteria regarding the inclusion of patients with GBM and/or other glioma subtype patients with FGFR1-TACC1, FGFR3-TACC3 fusion and/or activating mutation in FGFR1, 2 or 3. The number of allowed prior chemotherapy regimens was revised from two to unlimited. Reference to amplification or translocation was removed throughout the protocol.

- Section 1.1 (Background) was updated to include background information and rationale on inclusion of patients with other glioma subtypes. In addition, the rationale was provided on why FGFR amplification is a poor surrogate to detect FGFR fusions.
- Section 1.2.1.2 (Clinical experience) was updated with the most recent information as per latest version of the Investigator Brochure.
- Section 2 (Rationale) was updated with the additional rationale for treating glioma patients with FGFR inhibitor.
- Section 3 (Objectives and endpoints), Section 4 (Study design), Section 5 (Population) was updated to reflect the revisions to the study inclusion criteria.
- Section 5.2 (Inclusion criteria) inclusion criteria # 1, 3 and 6 were revised to reflect the changes in study inclusion criteria.
- Section 5.3 (Exclusion criteria) exclusion criteria # 17 and 19 were revised to reflect the changes in study exclusion criteria.

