- Section 6.2 (Dose modifications) was revised to update the management of hyperphosphatemia, renal toxicities, asymptomatic amylase and/or lipase elevation
- Section 6.3 (Concomitant medications) was updated to provide the latest recommendation on the management of the hyperphosphatemia.
- Section 7.1 (Study flow and visit schedule) was updated with the reduced frequency of ophthalmologic assessments.
- Section 7.1.1 (Molecular pre-screening) was updated with the number of required slides for molecular pre-screening.
- Section 10 (Statistical analysis) was revised based on the updated inclusion criteria.
- Appendix 1 and Appendix 2 (List of concomitant medications) was revised.

IRB/IEC/HA

A copy of this amended protocol will be sent to the Institutional Review Board (IRBs)/Independent Ethics Committee (IECs) and Health Authorities.

The changes described in this amended protocol require IRB/IEC approval prior to implementation.

The changes herein affect the Informed Consent. Sites are required to update and submit for approval a revised Informed Consent that takes into account the changes described in this protocol amendment.

Amendment 1

Amendment rationale

This amendment addresses changes requested following health authority review, and includes the following:

- The protocol exclusion criteria has been updated to indicate that patients with current evidence of corneal/keratopathy or retinal disorder are not eligible to participate. This update is being performed to align with the BGJ398 Investigator's Brochure (edition 6).
- The protocol will be updated to include ophthalmologic eye exam assessments in order to assess for early signs of corneal or retinal changes at baseline and monitor at periodic intervals. This update is being performed to completely align with the BGJ398 Investigator's Brochure (edition 6).
- The protocol will be updated to exclude patients with clinically significant hypokalemia. Clinically significant hypokalemia is known to increase the risk of dysfunction of ion channels in the myocardial cell membrane and therefore may increase the risk of TdP tachycardia.
- The protocol has specified a recovery period of at least 2 weeks following surgery before patients can receive BGJ398 treatment for patients enrolled in Group 2 (surgical group).

Also in this amendment, other sections have been modified for consistency and/or clarification, such as management of hyperphosphatemia.

Changes to the protocol

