6.2 Dose modifications

6.2.1 Dose modification and dose delay

For patients who do not tolerate the protocol-specified dosing schedule, dose adjustments are permitted in order to allow the patient to continue the study treatment. These changes must be recorded on the Dosage Administration Record CRF.

All dose modifications should be based on the worst preceding toxicity. The following guidelines need to be applied:

Each patient will be allowed up to 2 dose reductions. Patients must discontinue BGJ398 if toxicities persist following 2 dose reductions ([Table 6-2](#)) unless a continuation is allowed in discussion with Novartis.

Following resolution of toxicity to baseline or \leq grade 1, treatment is resumed at either the same or lower doses of study drugs as per the criteria in [Table 6-3](#). If treatment is resumed at the same doses of study drugs, and the same toxicity recurs with the same or worse severity regardless of duration, doses must be reduced to the next lower dose level ([Table 6-2](#)). If treatment is resumed at the lower doses of study drugs, and the same toxicity recurs with the same or worse severity, the patient must discontinue study treatment unless a continuation is allowed in discussion with Novartis.

If a patient requires a dose delay of > 14 consecutive days of BGJ398 from the intended day of the next scheduled dose, then the patient should be discontinued from the study treatment unless a continuation is allowed in discussion with Novartis.

Patients who discontinue the study for a study related adverse event or an abnormal laboratory value must be followed as described in [Table 6-3](#) and [Section 6.2.2](#).

In exceptional situations, study treatment may continue even if the patient experienced one of the treatment stopping rules. The decision to allow for continuation of treatment will be made on a case-by-case basis following discussion between Novartis and the Investigator.

Situations that may allow for continuation of treatment include but are not limited to the following.

- A dose delay of > 14 days has occurred, but the patient is clearly benefiting from study treatment (i.e., stable disease, partial response, or complete response) and it is the investigator's opinion that no safety concerns are present, after discussion with Novartis Medical Monitor, the patient may remain on the study treatment

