
Asymptomatic amylase and/or lipase elevation
 
Grade 3 (> 2.0 - 5.0 x ULN)
 
Grade 4 (>5.0 x ULN)
	
 ● Hold dose of BGJ398 until resolved to CTCAE Grade ≤ 2. ● ↓ 1 dose level of BGJ398 
For recurrent Grade 3 asymptomatic lipase or amylase elevation despite dose reduction, BGJ398 should be held and continuation of therapy should be discussed with the Novartis medical monitor following resolution to ≤ Grade 2
 
For any Grade 4 asymptomatic lipase or amylase elevation, BGJ398 should be held and continuation of therapy should be discussed with the Novartis medical monitor following resolution to ≤ Grade 2.
 
Note: A CT scan or other imaging study to assess the pancreas, liver, and gallbladder should be performed as clinically indicated within 1 week of the first occurrence of any CTCAE ≥ Grade 3 amylase and/or lipase.

Grade 4 (> 5.0 x ULN)	Discontinue patient from study treatment

Hyperphosphatemia
 
Serum phosphorus >5.5 – 7.0 mg/dL
 
Serum phosphorus > 7.0 mg/dL for more than 7 days despite maximal phosphate lowering therapy (Sevelamer) or single serum phosphorus >
	
Maintain dose level of BGJ398 and optimize phosphate lowering therapy as clinically indicated.
 
Hold BGJ398 dose until resolved to serum phosphorus ≤ 5.5 mg/dL.

Worst Toxicity CTCAE using the current active CTCAE version	Recommended Dose Modifications any time during a cycle of therapy

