
9.0 mg/dL regardless of duration or dose of phosphate lowering therapy (Sevelamer).
 
(Optimize/maximize dose and schedule of phosphate lowering therapy in accordance with package insert, country or institutional guidelines).
	
Restart BGJ398 at the same dose level with maximal phosphate binder dosing if the patient did not receive maximal phosphate binder dosing for serum phosphorus > 7.0 mg/dL for > 7 days.
 
Reduce one dose level of BGJ398 if the patient had received maximal phosphate lowering therapy for serum phosphorus >7.0 mg/dL for > 7 days or if patient had a one-time serum phosphorus of > 9.0 mg/dL. Restart BGJ398 with maximal phosphate binder dosing.
 
It is recommended that phosphate binder dosing continues during BGJ398 dose interruptions for hyperphosphatemia and that serum phosphorus values be monitored frequently, e.g. every 2-3 days.
 
Phosphate binder dosing should be held during the week off BGJ398 therapy each cycle (Days 22-28) and during BGJ398 dose interruptions for non-hyperphosphatemia adverse events.

Hypercalcemia Serum calcium grade 2
 
Serum calcium ≥ grade 3
	
Hold BGJ398 dose until resolved to grade 1 or baseline:
 
 • if resolved ≤ 7 days after suspending BGJ398, maintain dose level • if resolved > 7 days after suspending BGJ398, ↓ 1 dose level 
Discontinue patient from the study

Nervous system disorders	

Neurotoxicity Grade 2
 
Grade ≥ 3
	
Omit dose of BGJ398 until resolved to CTCAE Grade ≤ 1, then ↓ 1 dose level of BGJ398
 
Discontinue patient from study drug treatment

GI disorders	

Pancreatitis Grade ≥ 2
	
Discontinue patient from study drug treatment

Worst Toxicity CTCAE using the current active CTCAE version	Recommended Dose Modifications any time during a cycle of therapy

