7.2.2.5 Laboratory evaluations

Clinical laboratory analyses are to be performed by the local laboratory as indicated in [Table 7-1](#) and [Table 7-3](#). Laboratory tests will be collected and analyzed on the scheduled day, even if study treatment is being withheld. More frequent assessments may be performed at the discretion of the Investigator and if medically indicated, and should be recorded on the Unscheduled Visit eCRFs.

At any time during the study, abnormal laboratory parameters which are clinically relevant (e.g., require dose modification and/or interruption of study treatment, lead to clinical symptoms or signs, or require therapeutic intervention), whether specifically requested in the protocol or not, will be recorded on the Adverse Events eCRF page. Laboratory data will be summarized using the CTCAE (version 4.03).

Novartis must be provided with a copy of the laboratory's certification, and normal ranges for each parameter measured. In addition, if at any time a patient has laboratory parameters

obtained from a different outside laboratory, Novartis must be provided with a copy of the certification and normal ranges for that laboratory.

Table 7-3 Clinical laboratory parameters collection plan

Test Category	Test Name
Hematology	Hematocrit, Hemoglobin, Platelets, White blood cells, Differential (Basophils, Eosinophils, Lymphocytes, Monocytes, Neutrophils)
Biochemistry	Albumin, Alkaline phosphatase, ALT (SGPT), AST (SGOT), Calcium (Total), Chloride, Creatinine, Blood Urea Nitrogen (BUN) or Urea, Potassium, Sodium, Magnesium, Inorganic Phosphorous . Direct Bilirubin, Indirect Bilirubin, Total Bilirubin, direct/indirect bilirubin, Total Protein, Uric Acid, Amylase, Lipase.
Urinalysis	Macroscopic Panel (Dipstick) (Blood, Glucose, Ketones, pH, Protein, Specific Gravity). Microscopic Panel (Red Blood Cells, WBC).
Coagulation	Prothrombin time (PT) or International normalized ratio [INR]), Partial thromboplastin time (PTT),
Pregnancy Test	Serum hCG at screening; EOT and other times points serum hCG or urine.

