The **actual cumulative dose** refers to the total actual dose administered, over the duration for which the subject is on the study treatment as documented in the DAR (e)CRF.

For patients who did not take any drug the cumulative dose is by definition equal to zero.

Relative dose intensity

Actual dose intensity (ADI) for patients with non-zero duration of exposure is defined as follows:

$$\text{ADI (mg / day)} = \text{Actual Cumulative dose (mg)} / \text{Duration of exposure to study treatment (day)}.$$

For patients who did not take any drug the ADI is by definition equal to zero.

Planned dose intensity (PDI) is defined as follows:

$$\text{PDI (mg / day)} = \text{Planned Cumulative dose (mg)} / \text{Duration of exposure (day)}.$$

Relative dose intensity (RDI) is defined as follows:

$$\text{RDI} = \text{ADI (mg / day)} / \text{PDI (mg / day)}.$$

Dose reductions, interruptions or permanent discontinuations

The number of subjects who have dose reductions, dose interruptions, or dose permanent discontinuations, and the reasons, will be summarized. 'Dose Changed', 'Dose interrupted', and 'Dose permanently discontinued' fields from the DAR (e)CRF will be used to determine the dose reductions, dose interruptions, and permanent discontinuations, respectively. **Note:** planned 1 week off in dosing schedule will not be collected or counted as dose interruption. The corresponding field 'Reason' for dose changed, dose interrupted, and dose permanently discontinued will be used to summarize the reasons.

A dose reduction is defined as a decrease in total daily dose from the protocol planned dose, and a decrease from the previous non-zero dose, even if this decrease has been directly preceded by an interruption, and the dose change flag is checked. For example, in the sequence 125 mg – 0 mg – 100 mg, the 100 mg dose will be counted as a reduction.

A dose interruption is defined as an instance that no study drug (0 mg) is taken when the protocol planned dose is non-zero. For example, in the sequence 125 mg – 0 mg – 100 mg, the 0 mg dose will be counted as an interruption.

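### Protocol Table 6-3 gives two incompatible actions for asymptomatic Grade 4 amylase or lipase elevation: hold and discuss continuation, or discontinue

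*Protocol*

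**What the plan says.** The row of Protocol Table 6-3 headed for asymptomatic amylase and/or lipase elevation covers Grade 3 (above 2.0 and up to 5.0 x ULN) and Grade 4 (above 5.0 x ULN). Its Grade 4 instruction reads: "For any Grade 4 asymptomatic lipase or amylase elevation, BGJ398 should be held and continuation of therapy should be discussed" with the medical monitor after the value has come down to Grade 2 or lower.

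Directly below, before the hyperphosphatemia row, is a row with a grade, a threshold and an action but no toxicity name. The grade and threshold are again Grade 4, above 5.0 x ULN. The action is discontinuation of study treatment.

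Three other places bear on how to read this:

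- The Amendment 2 rationale: "The criteria for drug discontinuation due to asymptomatic increase in lipase have been relaxed". Its list of changes says Section 6.2 "was revised to update the management of hyperphosphatemia, renal toxicities, asymptomatic amylase and/or lipase elevation".
- Table 6-3, GI disorders: "Pancreatitis Grade ≥ 2" has its own row, with discontinuation as the action.
- Section 6.2.1: "In exceptional situations, study treatment may continue even if the patient experienced one of the treatment stopping rules", case by case, after discussion between the sponsor and the investigator.

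**The concern.** A stopping rule should give one action for one event. Here two adjacent rows give different actions for the same laboratory finding, and nothing says which governs.

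The trigger can turn up without symptoms, because the routine biochemistry panel in Protocol Table 7-3 includes "Total Protein, Uric Acid, Amylase, Lipase". A site that follows the labelled row will hold the drug and raise rechallenge once the value recovers. A site that follows the next row will end treatment and may never ask. At stake is whether patients with the same finding get the same chance to resume a drug that may be helping them, and whether sites apply the safety rule alike. Whichever row a site follows, a reader of the other row could call the action a protocol deviation.

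**Working it through.** No arithmetic applies. The check is a comparison of the two rows, followed by a search for anything in the documents that would reconcile them.

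**Step 1. The two rows side by side (Protocol Table 6-3).**

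| | Labelled row | Next row |
|---|---|---|
| Toxicity named | Asymptomatic amylase and/or lipase elevation | None |
| Grade and threshold | Grade 4, > 5.0 x ULN | Grade 4, > 5.0 x ULN |
| Immediate action | Stop drug (hold) | Stop drug (discontinue) |
| After recovery to Grade 2 or lower | Discuss continuation with the medical monitor | No provision |

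The grade and threshold are identical. The actions agree on the day of the finding and part afterwards.

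**Step 2. Could the second row belong to another toxicity?** The other liver and kidney rows based on ULN do not fit:

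- Creatinine: Grade 3 or higher starts above 3.0 x ULN.
- Bilirubin: Grade 3 or higher starts above 3.0 x ULN.
- AST/ALT: Grade 4 starts above 20.0 x ULN. The figure 5.0 x ULN appears there only as the lower limit of Grade 3.
- AST/ALT combined with bilirubin: 5.0 x ULN appears, but tied to a bilirubin condition and with no grade label.

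Hyperphosphatemia, the row that follows, is set in mg/dL. Only amylase/lipase pairs Grade 4 with > 5.0 x ULN.

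**Step 3. Could it be a rule for symptomatic elevation?** Possibly, but the row does not say so, and pancreatitis of Grade 2 or higher already has a discontinue row.

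**Step 4. Does a general rule decide between the rows?**

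- Section 6.2.1 and the note closing Table 6-3 base dose changes on the worst toxicity so far. That ranks events of different severity. Here the event and its grade are the same in both rows.
- The exception clause in Section 6.2.1 allows continuation past a stopping rule, but as an exception. The labelled row makes hold-and-discuss the standard action for any Grade 4 value. The clause does not say which row is the rule.
- The ongoing review of individual patient data in Section 8.6 may catch a case, but it does not settle the text.

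**Step 5. Is this only an amendment-log difference or an extraction fault?** No. Both instructions stand in the current table. The second row has its own grade, threshold and action, and no repeated page header separates it from the row above. The amendment text is used here only as evidence of what the sponsor intended.

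**The case against.** The strongest reply is that little turns on this. Both rows stop the drug immediately. On either path a restart needs a discussion with the sponsor: the labelled row requires it, and Section 6.2.1 allows it after any stopping rule. A delay of more than 14 days normally ends treatment anyway unless continuation is agreed, so a patient whose enzymes fall slowly usually reaches the same outcome under both rows. The column is also headed as recommended modifications. All of this stands, and it limits the point to the default on rechallenge. It does not remove the conflict, because a patient who recovers within 14 days still has two different instructions.

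The second reply is that calling the row a leftover goes beyond the evidence. This also stands. The Amendment 2 rationale speaks of lipase and of mild to moderate increases. It does not mention Grade 4 or amylase, and the superseded table is not available. A reader might take the amendment as proof that the row should go. It supports that reading but does not prove it, so the sponsor's medical team should confirm which action was meant.

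A third reply concerns reporting. The SAP says in Section 2.4.1: "The number of subjects who have dose reductions, dose interruptions, or dose permanent discontinuations, and the reasons, will be summarized". A reader might infer that the tolerability tables would misclassify events. The documents do not support that. The counts come from the dosing record, so they would correctly show what each site did. The tables would differ between sites only because conduct differed.

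**Conclusion.** The contradiction is real and confined to one stopping rule: asymptomatic Grade 4 amylase or lipase elevation has two actions that cannot both be followed. Its effect is limited to whether rechallenge is open by default and to consistent safety conduct across sites.

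No size in patients or percentage points is claimed. The documents do not report how often this event occurs, and a percentage based on one affected patient would show only the weight of one patient in a small set.

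Two broader readings are tempting and should not be drawn:

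- *That the efficacy result is at risk.* The sample size simulations, the success criteria and the PFS definition make no use of this rule. Patients who stop for reasons other than progression continue to be scanned every 8 weeks until progression, death or new anticancer therapy. A reader might also worry that a deviation would remove a patient from the Per-Protocol Set. The exclusions described in SAP Table 2-3 are unmet inclusion criteria and prohibited concomitant medication, not a dosing action after a laboratory finding. The conclusion assumes that list is applied as written.
- *That Table 6-3 is contradictory more widely.* The eye rows have a reading without conflict, because the stricter row sits under a retinal heading. In the phosphate rows, the worst-toxicity principle and the explicit reduction for a single value above 9.0 mg/dL largely settle the order.

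**What to change.** State one governing action for asymptomatic Grade 4 amylase or lipase elevation. The change most consistent with Amendment 2 is to delete the unlabelled Grade 4 row, leaving hold-and-discuss as the only instruction. If the sponsor's medical team meant the row for another event, such as symptomatic elevation, they should keep it and name that event in it.

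The cost is the deletion or labelling of one row at a protocol amendment. It needs no new data and no change to the sample size or the analysis.

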
Grade 3
 
Grade 4
	
Hold dose of BGJ398 until resolved to CTCAE Grade ≤ 1, then ↓ 1 dose level of BGJ398.
 
Discontinue patient from study treatment.

All dose modifications should be based on the worst preceding toxicity. Once a dose has been reduced it will not be increased at a later time even if there is no toxicity. Patients who require more than two dose reductions of BGJ398 will be discontinued from study drug treatment.
 
If a patient requires a dose delay of > 14 days from the intended day of the next scheduled dose of BGJ398 then study treatment must be stopped.
	

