6.2.3 Anticipated risks and safety concerns of the study drug

Eligibility criteria as well as specific dose modification and stopping rules are included in this protocol. Guidelines for prophylactic or supportive treatment for expected toxicities, including management of study-drug induced adverse events, i.e., hyperphosphatemia, and renal toxicities are provided in [Table 6-3](#). Refer to preclinical toxicity and or clinical data found in the [BGJ398 Investigator's Brochure].

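### Table 6-3 (Hyperphosphatemia): the same-dose restart is written for patients whom the row's own trigger does not hold unless a value exceeds 9.0 mg/dL

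*Protocol*

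**What the plan says.** All of the operative text is in the hyperphosphatemia row of Table 6-3 (protocol section 6.2.1).

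- **No hold.** Above 5.5 and up to 7.0 mg/dL, the dose is maintained and phosphate-lowering therapy is optimized.
- **Hold, first limb.** "Serum phosphorus > 7.0 mg/dL for more than 7 days despite maximal phosphate lowering therapy (Sevelamer").
- **Hold, second limb.** A single value above "9.0 mg/dL regardless of duration or dose of phosphate lowering therapy (Sevelamer"). Under either limb the drug is held until phosphorus is 5.5 mg/dL or lower.
- **Same-dose restart.** "Restart BGJ398 at the same dose level with maximal phosphate binder dosing if the patient did not receive maximal phosphate binder dosing", where the condition referred to is phosphorus above 7.0 mg/dL for more than 7 days.
- **Reduced restart.** "Reduce one dose level of BGJ398 if the patient had received maximal phosphate lowering therapy for serum phosphorus >7.0 mg/dL for > 7 days", or after a one-time value above 9.0 mg/dL.

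A bracketed note in the trigger cell tells the site to optimize or maximize the binder. It does not mention holding BGJ398.

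Section 6.2.3 confirms that this table is where the rule lives: guidelines "including management of study-drug induced adverse events, i.e., hyperphosphatemia, and renal toxicities are provided in" Table 6-3. Both section 6.2.1 and the table's closing note say that dose modifications follow the worst toxicity so far. The closing note adds: "Once a dose has been reduced it will not be increased at a later time even if there is no toxicity".

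**The concern.** A restart rule should apply to patients whom the trigger has stopped. Here the same-dose restart describes a patient on less-than-maximal binder, while the duration limb of the trigger requires maximal therapy. A site with a patient at, say, 8 mg/dL for more than 7 days on a moderate sevelamer dose finds no instruction to hold, but does find an instruction for how to restart. One investigator can continue and raise the binder; another can hold and restart at 125 mg. Each has support in the row.

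The row will be consulted often. Raised phosphorus is the drug's most frequent adverse event (section 1.2.1.2.1: 71.3% as a drug-related event in the phase I study, 74% as a treatment-emergent event). One dose-limiting toxicity at 125 mg, the starting dose here, was hyperphosphatemia lasting more than 14 days. In animals, raised phosphorus came with ectopic mineralization that was only partly reversible (section 1.2.1.1.2). Interruptions, reductions and dose intensity are tolerability endpoints in Table 3-1, so uneven handling across sites also enters reported results.

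**Working it through.** The check is one of logic. Take each relevant patient, apply the trigger, then see which restart condition is met.

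| Phosphorus history | Binder | Held by the trigger? | Same-dose condition met? | Reduction condition met? |
|---|---|---|---|---|
| >7.0 to 9.0 mg/dL, >7 days | Maximal | Yes (first limb) | No | Yes |
| >7.0 to 9.0 mg/dL, >7 days | Less than maximal | **No** | **Yes** | No |
| A value >9.0, not >7.0 for >7 days | Either | Yes (second limb) | No | Yes |
| A value >9.0, and >7.0 for >7 days | Maximal | Yes (both limbs) | No | Yes |
| A value >9.0, and >7.0 for >7 days | Less than maximal | Yes (second limb) | Yes | Yes |

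1. The two reduction conditions repeat the two hold limbs. Every patient held by the row is therefore sent to a reduction.
2. The only patient who meets the same-dose condition alone (second line) is not held.
3. The one held patient who also meets the same-dose condition (last line) meets the reduction condition too. The worst-preceding-toxicity rule settles this: the value above 9.0 mg/dL governs, and the dose is reduced.
4. The same-dose condition could be read more widely, as covering anyone who was not on maximal binder through more than 7 days above 7.0 mg/dL. The additional held patients are then those in the third line, with a value above 9.0 mg/dL. They are also sent to a reduction, so the result does not change.

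Next, does other text supply the missing hold? Section 6.2.1 sends resumption back to Table 6-3. Section 6.3.1 also refers to that table. Section 6.1.2 points to section 6.2.2, which covers follow-up of toxicities and has no phosphorus threshold. The table's row for other clinically significant adverse events is a catch-all, and its Grade 3 action (hold, then reduce) would contradict a same-dose restart. None of these resolves the mismatch.

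Each way of reading the row leaves some of it without effect. If everyone above 7.0 mg/dL for more than 7 days is held, the maximal-therapy condition in the trigger does nothing. If the binder is maximized first without a hold, the same-dose restart has nobody to restart.

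Frequency, from section 1.2.1.2.1 (data cut-off 15 March 2014, 3 weeks on/1 week off):

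- Elevated phosphorus: 17/25 = 0.68 (exact Clopper-Pearson 95% interval 0.465 to 0.851).
- Cycle 1 interruption or reduction: 4/25 = 0.16.

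The first figure shows how often the row may be opened. The second is closer to the consequence. Neither is broken down by phosphorus level, duration or binder dose, so neither gives the number of patients in the second line of the table.

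**The case against.** The best defence is that section 6.2.1 permits dose adjustments for patients who do not tolerate the schedule. An investigator who interrupts on that ground can use the same-dose rule to choose the restart level, so the clause is usable. That is fair, but such an interruption is discretionary. It supplies no hold rule, and discretion to hold or continue is exactly the inconsistency at issue. The column is headed as recommendations, yet section 6.2.1 says that the guidelines have to be applied.

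The safeguards are also real. Any value above 9.0 mg/dL is held, raised creatinine with hyperphosphatemia has its own monitoring and hold rules, binders are given prophylactically, and individual data are reviewed on an ongoing basis (section 8.6). They limit the harm but do not remove the contradiction.

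A reader might infer more than the documents support:

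- *That the trigger never holds a patient on less-than-maximal binder.* It does, through the second limb.
- *That the row has no precedence when both restart rules fit.* The worst-preceding-toxicity rule provides it.
- *That values above 7.0 and up to 9.0 mg/dL for 7 days or less are an equal gap.* The trigger excludes them by its duration condition, and the bracketed note covers the binder. An explicit line would help, but its absence is mostly missing detail.
- *That the effect on dose intensity can be given a size.* That needs the timing of onset and the binder response, which the documents do not report.
- *That a long hold caused by the mismatch ends treatment.* After a delay of more than 14 days, section 6.2.1 says "then the patient should be discontinued from the study treatment unless a continuation is allowed in discussion with Novartis".

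**Conclusion.** The row is wrong as written and should be corrected. The hold trigger and the same-dose restart contradict each other: no patient held by the row can be assigned a same-dose restart, and the patient for whom that restart was written is left without a clear instruction to hold or continue. This rests on the text alone and on no numerical assumption.

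The effect is on patient safety, consistent dosing across sites, and the descriptive tolerability endpoints. Its size cannot be estimated from the documents. The 68% and 16% above give context only, and come from a phase I study rather than this trial. PFS6 and its decision rule are not directly affected. The likely intention was to hold on level and duration and let binder dose decide the restart level, but the text does not say so, and only the sponsor can confirm it.

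**What to change.** Make the trigger and the restart rules agree, in one of two ways.

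**(a)** Hold BGJ398 for any phosphorus above 7.0 mg/dL for more than 7 days whatever the binder dose, and for any single value above 9.0 mg/dL. After recovery to 5.5 mg/dL or lower, restart with maximal binder: at the same dose if the binder had been less than maximal and no value exceeded 9.0 mg/dL, otherwise one level lower.

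**(b)** If binder maximization without a hold was intended, say so: above 7.0 and up to 9.0 mg/dL for more than 7 days on less-than-maximal binder, maintain BGJ398 and maximize the binder. Delete the same-dose restart.

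Either needs a protocol amendment under section 12.1, with ethics approval, to rewrite one table row. No threshold changes and no patients are added. Option (a) adds some short holds in patients whom the trigger now leaves on drug; option (b) adds none.

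Two optional clarifications could go in the same amendment. One is a line for values above 7.0 and up to 9.0 mg/dL lasting 7 days or less: maintain BGJ398, maximize the binder, and recheck every 2 to 3 days. The row now recommends that frequency only "during BGJ398 dose interruptions for hyperphosphatemia and that serum phosphorus values be monitored frequently, e.g. every 2-3 days", so this would add a few phosphorus draws. The other is to point section 6.1.2 to Table 6-3 instead of section 6.2.2.
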